#### 7.6.4 Investigator's Decision to Continue or Discontinue Treatment

At all times during the study the decision to continue iv, switch to po, or discontinue test article is made based on the patient response including the attainment of clinical stability and the clinical judgment of the investigator.

The investigator may use microbiological results (e.g., culture and susceptibility results) from the local microbiology laboratory to help guide therapy; however, investigator decisions to continue or discontinue test article should be based on *clinical response* rather than susceptibility results. For example, if a respiratory pathogen is detected after randomization that is not susceptible to omadacycline and/or moxifloxacin and the subject is stable or clinically improving, blinded study treatment may continue unless the investigator perceives an undue risk to the subject.

Similarly, if a viral respiratory pathogen is detected after randomization (including but not limited to SARS-CoV-2), study drug may be continued if the investigator continues to suspect co-infecting bacterial pathogen(s) and the subject is stable or clinically improving, and concomitant treatment for the viral pathogen may be administered as appropriate. Questions about individual cases should be discussed with the Medical Monitor prior to discontinuing study drug or administering additional antimicrobial agents, and decisions should be recorded in source documents.

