### 7.13 **Prohibited Therapy**

All investigational medications or devices used during the 30 days prior to Screening are prohibited.

All of the following therapies are excluded starting from the time of consent through EOT visit:

- More than 1 dose of a potentially therapeutic antibacterial agents (with potential activity against pathogens responsible for CABP) are prohibited for 72 hours prior to randomization through EOT, with the exception of cases where a subject is deemed a clinical failure during the course of the study and requires treatment with an additional antibacterial agent
- Subjects will be instructed to avoid taking antacids and multivitamins containing multivalent cations (eg, aluminum, magnesium, calcium, bismuth, iron, or zinc) for 4 hours before and within 4 hours after oral doses

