## 7.14 Permitted Treatments

All other treatments not specified as prohibited are permitted during the study. Subjects requiring additional or alternative antibacterial therapy for their CABP will be judged as Clinical Failures and test article will be discontinued. Further treatment for their infection is at the discretion of the investigator or the subject's health care provider and will be considered as a concomitant medication.

Subjects should be encouraged to contact site personnel before starting any new treatment.

For all treatments received by the subject during the study, relevant information must be recorded on the subject's eCRF.

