# 8.13.1.1 Evaluation of the Infection Under Study at the Early Clinical Response Assessment

The formal determination of the response to therapy at the ECR assessment (72 to 120 hours after administration of the first dose of test article) will be done programmatically using the investigator's assessment of the subject's symptoms associated with CABP entered into the eCRF. The investigator is not responsible for categorizing subjects as Clinical Success, Failure, or Indeterminate at the ECR assessment. The severity of the subject CABP symptoms of cough, sputum production, pleuritic chest pain and dyspnea will be evaluated on a 4-point scale (absent, mild, moderate, or severe) based upon the Community-Acquired Bacterial Pneumonia Subject Symptom Severity Guidance Framework for Investigator Assessment (see Appendix 3). A CABP subject symptom severity assessment should be completed at every scheduled evaluation with the exception of the Final Follow-up assessment (see Section 8.8 and Appendix 1). For subjects that have been switched to po test article and discharged from the hospital prior to Study Day 4, only 1 visit is required between Study Days 4 to 6 (see Appendix 1 for ECR study procedures). Subjects who remain hospitalized during the ECR phase should have the study procedures performed each day (see Appendix 1).

Clinical Success: at the ECR assessment will be defined as survival with improvement of at least 1 level (ie, severe to moderate, moderate to mild, mild to absent) compared to Screening in 2 of the 4 CABP symptoms (cough, sputum production, pleuritic chest pain, and dyspnea) with no worsening by at least 1 level in the other inclusion CABP symptoms. In order for the subject to be considered a Clinical Success, the subject may not meet any criteria for Clinical Failure or Indeterminate ECR.

Clinical Failure: defined as meeting any of the following criteria:

- There is no improvement by at least 1 level (ie, severe to moderate, moderate to mild, mild to absent) compared to Screening in 2 CABP symptoms.
- Any of the 4 CABP symptoms is worse (by at least 1 level) compared to Screening.
- The subject requires alternative (rescue) antibacterial treatment for CABP prior to the ECR assessment related to either (a) progression or development of new symptoms attributable to CABP or (b) development of infectious complications of CABP (eg, empyema, lung abscess).

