- The subject is receiving antibacterial therapy that may be effective for the infection under study for a different infection from the one under study.
- Discontinued study therapy due to an AE and received alternative antibacterial treatment for CABP prior to the ECR assessment.
- Death prior to the ECR assessment.

Indeterminate: the clinical response to test article could not be adequately inferred due to:

• Subject was not seen for the evaluation because they withdrew consent or were lost to follow-up.

• Other specified reason.

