### **12.6.1** Early Clinical Response Efficacy Variable

The Early Clinical Response can be Clinical Success, Clinical Failure or Indeterminate (defined in Section 8.13.1.1).

An Indeterminate Response is included in the denominator for the calculation of the percentage of subjects with a Clinical Success in the ITT population and thus, is essentially considered as a Clinical Failure for the purpose of the primary analysis for the FDA.

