The categories of Early Clinical Response are defined as follows:

Clinical Success: at the ECR assessment will be defined as survival with improvement of at least 1 level (ie, severe to moderate, moderate to mild, mild to absent) compared to baseline (Screening) in at least 2 CABP symptoms (cough, sputum production, pleuritic chest pain, and dyspnea) with no worsening by at least 1 level in the other CABP symptoms. In order for the subject to be considered a Clinical Success, the subject may not meet any criteria for Clinical Failure or Indeterminate ECR.

Clinical Failure: meeting any of the following criteria:

• There is no improvement by at least 1 level (ie, severe to moderate, moderate to mild, mild to absent) compared to baseline (Screening) in 2 CABP symptoms.

- Any of the 4 CABP symptoms is worse (by at least 1 level) compared to baseline (Screening).
- The subject requires alternative (rescue) antibacterial treatment for CABP prior to the ECR assessment related to either (a) progression or development of new symptoms attributable to CABP; (b) development of infectious complications of CABP (eg, empyema, lung abscess) or (c) discontinuation of study therapy due to an AE.
- The subject is receiving antibacterial therapy that may be effective for the infection under study for a different infection from the one under study.
- Death prior to the ECR assessment.

Indeterminate: the clinical response to test article could not be adequately inferred due to:

- Subject was not seen for the evaluation because s/he withdrew consent, or were lost to follow-up
- Other specified reason.

Assuming none of the above definitions of failure is met, the following cases will be considered an indeterminate response: Subjects with missing data such that an ECR Response cannot be determined; subjects who did not have at least 2 symptoms of CABP at baseline; subjects with an ECR assessment outside of the 72–120-time window. Since subjects with an indeterminate response are included in the denominator of the calculation of Clinical Success, these subjects are essentially Clinical Failures. For the ITT population, the proportion of ITT subjects with a Clinical Success is defined using the following formula:

Number of subjects with an Early Clinical Success

Number of subjects with an Early Clinical Failure + Number of subjects with a response of Indeterminate + Number of subjects with an Early Clinical Success

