5.2.1.1 Estimand Framework

An addendum to ICH E9 introduces the concept of an estimand which translates the trial objective into a precise definition of the treatment effect that is to be estimated. The description of the estimand includes 4 attributes: the population, the variable (or endpoint) to be obtained for each subject, the specification of how to account for intercurrent events (ICE) and the population-level summary for the variable. These attributes are described below:

	Early Clinical Response	
Population	ITT Population	
Variable/Endpoint	Programmatic determination of early clinical success	
Handling of intercurrent	Composite estimand as the following ICE's are	
events	incorporated into the variable/endpoint:	
	Receipt of alternative (rescue) therapy (failure)	

	 Receipt of antibiotic that may be effective for CABP for a different infection (failure) Death (failure)
Population-level summary	Difference between treatment groups in percentage of subjects with an early clinical sucess

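### The ECR failure definition in SAP 5.2.1 counts alternative antibacterial treatment for CABP only for three listed reasons, which is narrower than the SAP's own estimand row and protocol 7.14; the coding should be reconciled before unblinding

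*SAP*

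**What the plan says.** Four places deal with other antibacterial treatment for CABP and the ECR outcome.

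- **SAP 5.2.1, Clinical Failure.** "The subject requires alternative (rescue) antibacterial treatment for CABP prior to the ECR assessment related to either (a) progression or development of new symptoms", then (b) infectious complications and (c) stopping study therapy because of an adverse event. The list ends there.
- **Protocol 8.13.1.1.** The same three reasons. The adverse-event route has its own bullet: "Discontinued study therapy due to an AE and received alternative antibacterial treatment for CABP prior to the ECR assessment".
- **SAP 5.2.1.1, estimand table.** Among the intercurrent events built into the endpoint as failures: "Receipt of alternative (rescue) therapy (failure", with no reason attached.
- **Protocol 7.14.** "Subjects requiring additional or alternative antibacterial therapy for their CABP will be judged as Clinical Failures". No reason and no timepoint is attached, and additional as well as alternative therapy is covered.

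ECR is derived by program. Protocol 8.13.1.1 states: "The investigator is not responsible for categorizing subjects as Clinical Success, Failure, or Indeterminate at the ECR assessment". An Indeterminate result is a non-success in the primary analysis (protocol 12.6.1: "An Indeterminate Response is included in the denominator for the calculation of the percentage of subjects with a Clinical Success in the ITT population").

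**The concern.** A program-derived primary endpoint needs one code for each subject. Here the code for a subject given other antibacterial treatment for an unlisted reason depends on which text is followed. Protocol 7.14, and the estimand row on its face, give failure. The operational definition in SAP 5.2.1, which a programmer would implement, gives success if the symptoms have improved, or possibly Indeterminate. A success scored on another drug is not what the composite estimand describes. If the question is settled only once data are in hand, a primary-endpoint coding choice will have been made late.

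**Working it through.** **1. Trace one subject through SAP 5.2.1.** Suppose the subject was moved to another antibacterial for CABP before the ECR assessment. The reason was not progression, a complication, an adverse event or another infection. At 72 to 120 hours two symptoms have improved, none is worse, and the assessment is complete.

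| Rule | Result |
|---|---|
| Failure: too little improvement, or any worsening | not met |
| Failure: alternative treatment for (a), (b) or (c) | not met, reason unlisted |
| Failure: active antibacterial for a different infection | not met, given for CABP |
| Failure: death | not met |
| Indeterminate: missing data, fewer than 2 baseline symptoms, or out of window | not met |
| Indeterminate: not seen (consent withdrawn or lost) | not met |
| Indeterminate: *Other specified reason* | undefined |
| Success: at least 2 symptoms improved, none worse | met |

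The literal result is success unless the undefined item is applied. By contrast, success at the post-therapy evaluation (protocol 8.13.1.3) requires that no systemic antibacterial other than test article was received. ECR success carries no such condition.

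**2. Can the case arise?** Protocol 7.6.4 foresees it in individual cases: "Questions about individual cases should be discussed with the Medical Monitor prior to discontinuing study drug or administering additional antimicrobial agents". Two passages limit it. Section 7.6.4 bases decisions on clinical response, and section 7.13 bars more than one dose of a potentially therapeutic antibacterial through end of treatment, "with the exception of cases where a subject is deemed a clinical failure during the course of the study". The documents give no count, so the sizes below are assumptions.

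**3. Reproduce the planned power.** Inputs from SAP 5.1.1: 670 subjects at 1:1, so n = 335 per arm; success p = 0.80 in both arms; margin 0.10; one-sided alpha 0.025. Farrington-Manning:

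power = Φ[(0.10 − 1.96·s0) / s1], where s0 = √{[q1(1−q1) + q2(1−q2)]/n}, s1 = √{2p(1−p)/n}, and q1, q2 are the maximum-likelihood rates under q1 − q2 = −0.10.

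- q1 = 0.7411, q2 = 0.8411
- s0 = √[(0.1919 + 0.1337)/335] = 0.03117
- s1 = √(0.32/335) = 0.03091
- power = Φ[(0.10 − 0.0611)/0.03091] = Φ(1.259) = 89.6%, as stated in the SAP

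**4. Balanced recoding from success to failure.** Put p = 0.80 − k in both arms. For k = 0.01, s0 = 0.03169 and s1 = 0.03147, so power = Φ[(0.10 − 0.0621)/0.03147] = Φ(1.204) = 88.6%.

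| Recoded in each arm | Power |
|---|---|
| 0 | 89.6% |
| 0.5% | 89.1% |
| 1% | 88.6% |
| 2% | 87.6% |
| 3% | 86.6% |

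For type I error, the true rates are set at the margin (0.70 v 0.80) and both arms are raised by 0.5, 1, 2 or 3 points, as the looser coding would do. The result is 2.5% each time.

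**5. How near the margin must the result be?** The primary interval is the unstratified Miettinen-Nurminen 95% interval (SAP 9.1). One subject is 1/335 = 0.30 points.

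- 268/335 in each arm: lower limit −6.1 points. Moving 7 subjects in each arm (261/335 v 261/335) gives −6.3.
- Extreme hypothetical, with all net recoding in the omadacycline arm. From 268/335 v 268/335, 12 recodes give −9.85 and 13 (13/335 = 3.9%) give −10.2. From the earlier-study counts in SAP Table 1 (270/329 v 279/331) the limit starts at −8.0; 6 recodes give −9.9 and 7 (7/329 = 2.1%) give −10.2.

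**The case against.** A reader might infer that nothing in the plan says how an unlisted reason is coded. That goes too far. Protocol 7.14 says failure, and so does the estimand row on its face. The fault is that the operational definition does not carry this through.

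The estimand row is also weaker evidence of conflict than it looks. It describes its events as built into the endpoint defined just before it, and reuses that bullet's term, so it may be a summary of 5.2.1. This stands. Protocol 7.14 is separate text and does not depend on that reading, although it is a general section that does not name ECR.

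Success is not the only possible reading of 5.2.1 either. A response on another drug could be said not to be inferable for test article, which leads to *Other specified reason*, and Indeterminate and failure count alike in the primary analysis. This also stands, but the item is undefined and nothing ties it to this event.

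A reader might further infer a bias toward non-inferiority from the one-arm counts in step 5. The documents describe no mechanism by which unlisted reasons would fall in one arm of a double-blind trial. Those counts show only how close a result would have to be.

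Nor would the subjects be untraceable. SAP 9.1 already summarises reasons for failure and for Indeterminate by arm, protocol 12.5 gives reasons for antibiotic receipt, and SAP 7.1 plans full listings. The gap is for those coded success: no planned table isolates them in the ITT population, and the post-dose antibacterial tables with reasons in SAP 12.2 are limited to the CE-EOT and CE-PTE populations.

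**Conclusion.** The point holds as an inconsistency in the coding of the primary endpoint that should be fixed. SAP 5.2.1 is narrower than protocol 7.14 and than the estimand row as worded, and its literal result for an improved subject with an unlisted reason is success. The size is probably small: about 1 point of power per 1% recoded and no change in type I error. This assumes the planned 80% success rate, 335 per arm, and recoding balanced across arms. The coding would change the conclusion only if the result already lay near −10 points. The documents give neither the number of such subjects nor a direction of bias, and they do not support a claim that the primary analysis is invalid.

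**What to change.** Before unblinding, state in SAP 5.2.1, for endpoint coding only, that a subject who received additional or alternative systemic antibacterial therapy for CABP after the first dose and before the ECR assessment used in the analysis is coded Clinical Failure whatever the reason. Then:

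- Note that this applies protocol 7.14 and is wider than the list in protocol 8.13.1.1. Otherwise the new SAP text would create a mismatch of its own.
- State whether a single dose counts. Section 7.14 sets no minimum, whereas 7.13 bars more than one dose.
- Define what *Other specified reason* covers and who applies it.
- Show these subjects as a separate line, by arm, in the reasons-for-failure summary already planned in SAP 9.1.

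Failure is preferable to Indeterminate because the sensitivity analysis in protocol 12.6.4 re-scores every Indeterminate as a success; the SAP 9.2 version re-scores only lost or missing subjects.

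The cost is one or two sentences, a small change to the ECR derivation and one table line, using data already collected. The downside is slightly lower observed success rates and the loss of power shown above. No protocol edit is proposed, since that would need an amendment (protocol 13.6.2). Nothing here changes when such treatment may be given.

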5.2.1.1 Estimand Framework

An addendum to ICH E9 introduces the concept of an estimand which translates the trial objective into a precise definition of the treatment effect that is to be estimated. The description of the estimand includes 4 attributes: the population, the variable (or endpoint) to be obtained for each subject, the specification of how to account for intercurrent events (ICE) and the population-level summary for the variable. These attributes are described below:

	Early Clinical Response	
Population	ITT Population	
Variable/Endpoint	Programmatic determination of early clinical success	
Handling of intercurrent	Composite estimand as the following ICE's are	
events	incorporated into the variable/endpoint:	
	Receipt of alternative (rescue) therapy (failure)	

	 Receipt of antibiotic that may be effective for CABP for a different infection (failure) Death (failure)
Population-level summary	Difference between treatment groups in percentage of subjects with an early clinical sucess

5.2.2 Secondary Efficacy Outcomes

5.2.2.1 Investigators Assessment of Clinical Response

The investigator will make an assessment of Clinical Response at the EOT and PTE Visits, based on the definitions below. The secondary efficacy outcome is clinical response at PTE based on the investigator assessments at the EOT and PTE Visits in the ITT and CE-PTE populations as defined in Table .

EOT Visit

At the EOT Visit (on the calendar day of, or within 2 days following the last dose of test article), the investigator will indicate the clinical status of the infection under study as detailed below.

Clinical Success:

- The subject is alive and the infection is sufficiently resolved such that further antibacterial therapy is not needed.
 - These subjects may have some residual findings related to infection (ie, cough) requiring ancillary (ie, non-antibiotic) treatment (eg, expectorant).
- In order for the subject to be considered a Clinical Success at EOT, the subject may not meet any criteria for Clinical Failure or Indeterminate at EOT.

Clinical Failure:

- The subject requires alternative antibacterial treatment for CABP prior to EOT related to either
 - progression or development of new symptoms to CABP, or
 - development of infectious complications of CABP (eg, empyema, lung abscess), or
 - \circ subject developed an AE that required discontinuation of study therapy prior to the EOT.

Other reasons for clinical failure are:

- Subject is receiving antibacterial therapy that may be effective for the infection under study for a different infection from the one under study.
- Death prior to EOT.

Indeterminate:

- The clinical response to test article could not be adequately inferred due to:
 - Subjects were not seen for EOT evaluation because they withdrew consent, were lost to follow-up, other reason (specify).
 - Other specified reason.

PTE Visit

At the PTE Visit (5 to 10 days after the subject's last day of study therapy) the investigator will indicate one of the following outcomes relating to the primary infection under study:

Clinical Success:

- Survival after completion of a test article regimen without receiving any systemic antibacterial therapy other than test article;
- Resolution of signs and symptoms of the infection present at Screening with no new symptoms or complications attributable to CABP; and
- No need for further antibacterial therapy.

Clinical Failure:

- The subject requires alternative antibacterial treatment for CABP prior to PTE related to either:
 - o progression or development of new symptoms of CABP, or
 - o development of infectious complications of CABP (eg, empyema, lung abscess).

Other reasons for clinical failure are:

- The subject is receiving antibiotics that may be effective for the infection under study for a different infection from the one under study.
- Death prior to PTE.

Indeterminate:

• The clinical response to test article could not be adequately inferred due to:

- Subjects were not seen for PTE evaluation because they withdrew consent, were lost to follow-up, other (specify).
- Other specified reason.

The efficacy outcome of Clinical Response at PTE is determined as follows from the investigator's assessments at the EOT and PTE Visits:

Table 4.Investigator's Assessment of Clinical Response

EOT Visit	PTE Visit	Clinical Response at PTE Visit
Success	Success	Success
Success	Failure	Failure
Success	Indeterminate	Indeterminate
Failure	Success	Failure
Failure	Failure	Failure
Failure	Indeterminate	Failure
Indeterminate	Success	Indeterminate
Indeterminate	Failure	Failure
Indeterminate	Indeterminate	Indeterminate

Abbreviations: EOT = end of treatment; PTE = post-therapy evaluation.

For the ITT population, the proportion of ITT subjects with a Clinical Success is defined using the following formula (where the denominator adds to the total number of subjects in the ITT population):

Number of subjects with Clinical Success

(Number of subjects with Clinical Success + Number of subjects with a Clinical Failure + Number of subjects with an Indeterminate response)

By definition, subjects in the CE-EOT and CE-PTE populations cannot have an Indeterminate response. Thus, for the CE-EOT and CE-PTE populations, the proportion of subjects with a Clinical Success is defined using the following formula:

Number of subjects with Clinical Success

(Number of subjects with Clinical Success + Number of subjects with a Clinical Failure)

